## **Blood donation**

Subjects should not donate blood while participating in this study, or for at least 90 days following the last infusion of MEDI4736 or until after 4-5X the half-life of Tremelimumab, whichever occurs longest.

## 4.3.3 Permitted concomitant medications

- Investigators may prescribe concomitant medications or treatments (e.g., acetaminophen, diphenhydramine) deemed necessary to provide adequate prophylactic or supportive care
- Concurrent use of hormones for non-cancer-related conditions (e.g., insulin for diabetes and hormone replacement therapy) is acceptable.
- Local treatment of isolated lesions for palliative intent is acceptable (e.g., by local surgery or radiotherapy)
- Use of immunosuppressive medications for the management of investigational product-related AEs or in subjects with contrast allergies is acceptable. In addition, use of inhaled and intranasal corticosteroids is permitted. A temporary period of steroids will be allowed for different indications, at the discretion of the principal investigator (e.g., chronic obstructive pulmonary disease, radiation, nausea, etc.). Dexamethasone may be used but attempts should be made to keep
it less than 4 mg/day.

• Inactivated vaccines, are permitted.

## 4.3.4 Prohibited concomitant medications

The following medications are considered exclusionary during the study.

- Any investigational anticancer therapy other than the protocol specified therapies
- Any concurrent chemotherapy, radiotherapy (except palliative radiotherapy), immunotherapy, biologic or hormonal therapy for cancer treatment, other than any stated comparator or combination regimens.)
- Immunosuppressive medications including methotrexate, azathioprine, and Tumor Necrosis Factor alpha-blockers (TNF-α blockers).
- Enzyme inducing anti-convulsants (e.g.: Carbamazepine, Phenytoin, Primidone, Topiramate). Please check with PI if have further questions.
- Live attenuated vaccines within 30 days of MEDI4736 and/or Tremelimumab dosing (i.e., 30 days prior to the first dose, during treatment with MEDI4736 and/or Tremelimumab and for 30 days post discontinuation of MEDI4736 and/or Tremelimumab).

# 4.4 Toxicity Management & Dose Delays/Modifications

Any patient who receives at least one dose of study therapy will be evaluable for toxicity endpoints. Each patient will be assessed for the development of toxicity according to the timeframe referenced in the Schedule of Events table. Toxicity will be assessed according to Common Terminology Criteria for Adverse Events (CTCAE) version 4.03. Following the first dose of MEDI4736 and/or tremelimumab, subsequent administration of MEDI4736 and/or tremelimumab can be modified based on toxicities observed (see Table 1, 2, and 3 below). Dose reductions are not permitted.

# Dosing Modification and Toxicity Management Guidelines for Immune-Mediated, Infusion-Related, and Non-Immune–Mediated Reactions (MEDI4736 Monotherapy or Combination Therapy With Tremelimumab or Tremelimumab Monotherapy)

General Considerations		
Dose Modifications	Toxicity Management	
Dose Modifications         Drug administration modifications of study         drug/study regimen will be made to manage         potential immune-related AEs based on         severity of treatment-emergent toxicities         graded per NCI CTCAE v4.03.         In addition to the criteria for permanent         discontinuation of study drug/study         regimen based on CTC grade/severity         (table below), permanently discontinue         study drug/study regimen for the following         conditions:	
 
It is recommended that management of immune-mediated adverse events         (imAEs) follows the guidelines presented in this table:
 
It is possible that events with an inflammatory or immune mediated mechanism could occur in         nearly all organs, some of them not noted specifically in these guidelines.
 
Whether specific immune-mediated events (and/or laboratory indicators of such events) are         noted in these guidelines or not, patients should be thoroughly evaluated to rule out any         alternative etiology (e.g., disease progression, concomitant medications, and infections) to a         possible immune-mediated event. In the absence of a clear alternative etiology, all such events         should be managed as if they were immune related. General recommendations follow.
 
Symptomatic and topical therapy should be considered for low-grade
 
	

 
Inability to reduce corticosteroid to a dose of ≤10 mg of prednisone per day (or equivalent) within 12 weeks after last dose of study drug/study regimen.
 
Recurrence of a previously experienced Grade 3 treatment- related AE following resumption of dosing.
 
	
 
(Grade 1 or 2, unless otherwise specified) events.
 
For persistent (>3 to 5 days) low-grade (Grade 2) or severe (Grade ≥3) events, promptly start prednisone 1 to 2 mg/kg/day PO or IV equivalent.
 
Some events with high likelihood for morbidity and/or mortality – e.g., myo-carditis, or other similar events even if they are not currently noted in the guidelines – should progress rapidly to high dose IV corticosteroids (methylprednisolone at 2 to 4 mg/kg/day) even if the event is Grade 2, and if clinical suspicion is high and/or there has been clinical confirmation. Consider, as necessary, discussing with the study physician, and promptly pursue specialist consultation.
 
	
Grade 1: No dose modification Grade 2: Hold study drug/study regimen dose until Grade 2 resolution to Grade ≤1. If toxicity worsens, then treat as Grade 3 or Grade 4. Study drug/study regimen	
 
If symptoms recur or worsen during corticosteroid tapering (28 days of taper), increase the corticosteroid dose (prednisone dose [e.g., up to 2 to 4 mg/kg/day PO or IV equivalent]) until stabilization or improvement of symptoms, then resume corticosteroid tapering at a slower rate (>28 days of taper).
 
More potent immunosuppressives such as TNF inhibitors
 
	

can be resumed once event stabilizes to         Grade ≤1 after completion of steroid         taper. Patients with endocrinopathies who         may require prolonged or continued         steroid replacement can be retreated with         study drug/study regimen on the         following conditions:         1. The event stabilizes and is         controlled.         2. The patient is clinically         stable as per Investigator         or treating physician's         clinical judgement.         3. Doses of prednisone are at         ≤10 mg/day or equivalent.         Grade 3: Depending on the individual toxicity,         study drug/study regimen may be         permanently discontinue study         drug/study regimen. Note: For Grade ≥3         asymptomatic amylase or lipase levels,         hold study drug/study regimen, and if         complete work up shows no evidence of         pancreatitis, study drug/study regimen         may be continued or resumed. Note:         Study drug/study regimen should be         permanently discontinued in Grade 3         events with high likelihood for morbidity         and/or mortality – e.g., myocarditis, or         other similar events even if they are not         currently noted in the guidelines. </td 
 
e.g infliximab(also refer to individual sections of the imAEs for specific type of immunosuppressive) should be considered for events not responding to systemic steroids. Progression to use of more potent immunosuppressives should proceed more rapidly in events with high likelihood for morbidity and/or mortality – e.g., myocarditis, or other similar events even if they are not currently noted in the guidelines – when these events are not responding to systemic steroids.
 
With long-term steroid and other immunosuppressive use, consider need for Pneumocystis jirovecii pneumonia (PJP, formerly known as Pneumocystis carinti pneumonia) prophylaxis, gastrointestinal protection, and glucose monitoring.
 
Discontinuation of study drug/study regimen is not mandated for Grade 3/Grade 4 inflammatory reactions attributed to local tumor response (e.g., inflammatory reaction at sites of metastatic disease and lymph nodes). Continuation of study drug/study regimen in this situation should be based upon a benefit-risk analysis for that patient.
 
	
 
e.g infliximab(also refer to individual sections of the imAEs for specific type of immunosuppressive) should be considered for events not responding to systemic steroids. Progression to use of more potent immunosuppressives should proceed more rapidly in events with high likelihood for morbidity and/or mortality – e.g., myocarditis, or other similar events even if they are not currently noted in the guidelines – when these events are not responding to systemic steroids.
 
With long-term steroid and other immunosuppressive use, consider need for Pneumocystis jirovecii pneumonia (PJP, formerly known as Pneumocystis carinti pneumonia) prophylaxis, gastrointestinal protection, and glucose monitoring.
 
Discontinuation of study drug/study regimen is not mandated for Grade 3/Grade 4 inflammatory reactions attributed to local tumor response (e.g., inflammatory reaction at sites of metastatic disease and lymph nodes). Continuation of study drug/study regimen in this situation should be based upon a benefit-risk analysis for that patient.
 


permanently discontinued in Grade 2 events with high likelihood for morbidity	
and/or mortality – e.g., myocarditis, or other similar events even if they are not currently noted in the guidelines – when	
they do not rapidly improve to Grade <1 upon treatment with systemic steroids and following full taper	
Note: There are some exceptions to permanent discontinuation of study drug for Grade 4 events(i.e hyperthyroidism, hypothyroidism, Type 1 diabetes mellitus)	

AE Adverse event; CTC Common Toxicity Criteria; CTCAE Common Terminology Criteria for Adverse Events; imAE immune-mediated adverse event; IV intravenous; NCI National Cancer Institute; PO By mouth.

Pediatric Considerations			
Dose Modifications	Toxicity Management		
The criteria for permanent discontinuation of study drug/study regimen based on CTC grade/severity is the same for pediatric patients as it is for adult patients, as well as to permanently discontinue study drug/study regimen if unable to reduce corticosteroid ≤ a dose equivalent to that required for corticosteroid replacement therapy within 12 weeks after last dose of study drug/study regimen	
 
All recommendations for specialist consultation should occur with a pediatric specialist in the specialty recommended.
 
The recommendations for dosing of steroids (i.e., mg/kg/day) and for IV IG and plasmapheresis that are provided for adult patients should also be used for pediatric patients.
 
The infliximab 5 mg/kg IV dose recommended for adults is the same as recommended for pediatric patients ≥ 6 years old. For dosing in children younger than 6 years old, consult with a pediatric specialist.
 
For pediatric dosing of mycophenolate mofetil, consult with a pediatric specialist.
 
		

 
With long-term steroid and other immunosuppressive use, consider need for PJP prophylaxis, gastrointestinal protection, and glucose monitoring
 

Specific Immune-Mediated Reactions			
Adverse Events	Severity Grade of the Event (NCI CTCAE version 4.03)	Dose Modifications	Toxicity Management
Pneumonitis/Interstitial Lung Disease (ILD)	Any Grade	General Guidance	
 
For Any Grade:
 
-Monitor patients for signs and symptoms of pneumonitis or ILD (new onset or worsening shortness of breath or cough). Patients should be evaluated with imaging and pulmonary function tests, including other diagnostic procedures as described below.
 
-Initial work-up may include clinical evaluation, monitoring of oxygenation via pulse oximetry (resting and exertion), laboratory work-up , and high-resolution CT scan
 

	Grade 1 (asymptomatic, clinical or diagnostic observations only; intervention not indicated)	No dose modifications required. However, consider holding study drug/study regimen dose as clinically appropriate and during diagnostic work-up for other etiologies.	
 
For Grade 1 (radiographic changes only):
 
Monitor and closely follow up in 2 to 4 days for clinical symptoms, pulse oximetry (resting and exertion), and laboratory work-up and then as clinically indicated.
 
Consider Pulmonary and Infectious disease consult.
 

Grade 2 (symptomatic medical intervention indicated;limiting instruemental ADL)	
 
Hold study drug/study regimen dose until
 
Grade 2 resolution to
 
Grade ≤1.
 
If toxicity worsens, then treat as Grade 3 or Grade 4.
 
If toxicity improves to Grade ≤1, then the decision to reinitiate study drug/study regimen will be based upon treating physician's clinical judgment and after completion of steroid taper.
 
	
 
For Grade 2 (mild to moderate new symptoms): 
 
Monitor symptoms daily and consider hospitalization.
 
 
 
Promptly start systemic steroids (e.g., prednisone 1 to 2 mg/kg/day PO or IV equivalent).
 
Reimage as clinically indicated.
 
If no improvement within 3 to 5 days, additional workup should be considered and prompt treatment with IV methylprednisolone 2 to 4 mg/kg/day started.
 
If still no improvement within 3 to 5 days despite IV methylprednisolone at 2 to 4 mg/kg/day, promptly start immunosuppressive therapy such as TNF inhibitors (e.g., infliximab at 5 mg/kg every 2 weeks). Caution: It is important to rule out sepsis and refer to infliximab label for general guidance using infliximab.
 
Once the patient is improving, gradually taper steroids over ≥28 days and consider prophylactic antibiotics, antifungals, or anti-PJP treatment (refer to current NCCN guidelines for treatment of cancer-related infections[Category 2B recommnedation]a
 
Consider pulmonary and infectious disease consult
 
Consider, as necessary, discussing with study physician.
 

	Grade 3 or 4		For Grade 3 or 4 (severe or new symptoms, new/worsening hypoxia, life-threatening):
	(Grade 3:severe symptoms;limiting self- care ADL;oxygen indicated) (Grade4:life-threatening respiratory compromise; urgent intervention indicated[e.g.,tracheostomy or intubation])	Permanently discontinue study drug/study regimen.	
 
Promptly initiate empiric IV methylprednisolone 1 to 4 mg/kg/day or equivalent.
 
Obtain Pulmonary and Infectious disease consult; consider, as necessary, discussing with study physician.
 
Hospitalize the patient.
 
Supportive care (e.g., oxygen).
 
If no improvement within 3 to 5 days, additional workup should be considered and prompt treatment with additional immunosuppressive therapy such as TNF inhibitors (e.g., infliximab at 5 mg/kg every 2 weeks' dose) started. Caution: rule out sepsis and refer to infliximab label for general guidance before using infliximab.
 
Once the patient is improving, gradually taper steroids over ≥28 days and consider prophylactic antibiotics, antifungals, and, in particular, anti-PJP treatment (refer to current NCCN guidelines for treatment of cancer-related infections[Category 2B recommendation]).a
 

Diarrhea/Colitis	Any Grade	General Guidance	For Any Grade: -Monitor for symptoms that may be related to diarrhea/enterocolitis (abdominal pain, cramping, or changes in bowel habits such as increased frequency over baseline or blood in stool) or related to bowel perforation (such as sepsis,peritoneal signs, and ileus). -Patients should be thoroughly evaluated to rule out any alternative etiology(e.g disease progression, other medications,or infections), including testing for clostridium difficile toxin,etc. -Steroids should be considered in the absence of clear alternative etiology, even for low-grade events, in order to prevent potential progression to higher grade event. -Use analgesics carefully;they can mask symptoms of perforation and peritonitis.

Grade 1		For Grade 1:
(Diarrhea: stool frequency of <4 over baseline per day) (Colitis: asymptomatic; clinical or diagnostic observations only)	No dose modifications.	-Monitor closely for worsening symptoms. -Consider symptomatic treatment, including hydration, electrolyte replacement, dietary changes (e.g., American Dietetic Association colitis diet), and loperamide. Use probiotics as per treating physician's clinical judgment
		For Grade 2:
Grade 2 (Diarrrhea: stool frequency of 4 to 6 over baseline per day)(Colitis:abdominal	Hold study drug/study regimen until resolution to Grade ≤1 • If toxicity worsens,	
 
-Consider symptomatic treatment, including hydration, electrolyte replacement, dietary changes (e.g., American Dietetic Association colitis diet), and loperamide and/or budesonide.
 
Promptly start prednisone 1 to 2 mg/kg/day PO or IV
 

pain;mucus or blood in stool)	
 
then treat as Grade 3 or Grade 4.
 
If toxicity improves to Grade ≤1, then study drug/study regimen can be resumed after completion of steroid taper.
 
	
 
If event is not responsive within 3 to 5 days or worsens despite prednisone at 1 to 2 mg/kg/day PO or IV equivalent, GI consult should be obtained for consideration of further workup, such as imaging and/or colonoscopy, to confirm colitis and rule out perforation, and prompt treatment with IV methylprednisolone 2 to 4 mg/kg/day started.
 

		- If still no improvement within 3 to 5 days despite 2 to 4 mg/kg IV methylprednisolone, promptly start immunosuppressives such as infliximab at 5 mg/kg once every 2 weeks a . Caution: it is important to rule out bowel perforation and refer to infliximab label for general guidance before using infliximab.
		
 
Consider, as necessary, discussing with study physician if no resolution to Grade ≤1 in 3 to 4 days.
 

		
 
Once the patient is improving, gradually taper steroids over ≥28 days and consider prophylactic antibiotics, antifungals, and anti-PJP treatment (refer to current NCCN guidelines for treatment of cancer-related
 

			infections [Category 2B recommendation]). a
	Grade 3 or 4 (Grade 3 diarrhea: stool frequency of ≥7 over baseline per day; Grade 4 diarrhea: life threatening consequences) (Grade 3 colitis: severe abdominal pain, change in bowel habits, medical intervention indi- cated, peritoneal signs; Grade 4 colitis: life- threatening consequences, urgent intervention indicated)	Grade3 Permanently discontinue study drug/study regimen for Grade 3 if toxicity does not improve to Grade ≤1 within 14 days; study drug/study regimen can be resumed after completion of steroid taper. Grade 4 Permanently discontinue study drug/study regimen.	
 
For Grade 3 or 4:
 
Promptly initiate empiric IV methylprednisolone 2 to 4 mg/kg/day or equivalent.
 
Monitor stool frequency and volume and maintain hydration.
 
Urgent GI consult and imaging and/or colonoscopy as appropriate.
 
If still no improvement within 3 to 5 days of IV methylprednisolone 2 to 4 mg/kg/day or equivalent, promptly start further immunosuppressives (e.g., infliximab at 5 mg/kg once every 2 weeks). Caution: Ensure GI consult to rule out bowel perforation and refer to infliximab label for general guidance before using infliximab.
 
Once the patient is improving, gradually taper steroids over ≥28 days and consider prophylactic antibiotics, antifungals, and anti-PJP treatment (refer to current NCCN guidelines for treatment of cancer-related infections [Category 2B recommendation]).a
 

Hepatitis (elevated LFTs) Infliximab should not be used for management of immune-related hepatitis	Any Grade	General Guidance	For Any Grade: - Monitor and evaluate liver function test: AST, ALT, ALP, and TB. - Evaluate for alternative etiologies (e.g viral hepatitis,disease progression,concomitant medications).

PLEASE SEE shaded area	Grade 1		For Grade 1:
immediately below this section to find guidance for management of "Hepatitis (elevated LFTS)" in HCC patients	(Based on ULN regardless of baseline LFT) (AST or ALT >ULN and ≤3.0×ULN and/or TB > ULN and ≤1.5xULN)	
 
No dose- modifications.
 
If it worsens, then treat as Grade 2 event.
 
	Continue LFT monitoring per protocol.
	Grade 2 (Based on ULN regardless of baseline LFT) (AST or ALT >3.0×ULN and ≤5.0×ULN and/or TB >1.5×ULN and ≤3.0×ULN)	
 
Hold study drug/study regimen dose until Grade 2 resolution to Grade ≤1.
 
If toxicity worsens, then treat as Grade 3 or Grade 4.
 
If toxicity improves to Grade ≤1 or baseline, resume study drug/study regimen after completion of steroid taper.
 
	
 
For Grade 2:
 
Regular and frequent checking of LFTs (e.g., every 1 to 2 days) until elevations of these are improving or resolved.
 
If no resolution to Grade ≤1 in 1 to 2 days, consider, as necessary, discussing with study physician.
 
If event is persistent (>3 to 5 days) or worsens, promptly start prednisone 1 to 2 mg/kg/day PO or IV equivalent.
 
If still no improvement within 3 to 5 days despite 1 to 2 mg/kg/day of prednisone PO or IV equivalent, consider additional work up and start prompt treatment with IV methylprednisolone 2 to 4 mg/kg/day.
 
If still no improvement within 3 to 5 days despite 2 to 4 mg/kg/day of IV methylprednisolone, promptly start immunosuppressives (i.e., mycophenolate mofetil).a Discuss with study physician if mycophenolate mofetil is not available. Infliximab should NOT be used.
 
Once the patient is improving, gradually taper steroids over ≥28 days and consider prophylactic antibiotics, antifungals, and anti-PJP treatment (refer to current NCCN guidelines for treatment of cancer-related infections[Category 2B recommendation])a
 

Grade 3 or 4	For Grade	For Grade 3 or 4:
(Based on ULN regardless of baseline LFT) (Grade 3: AST or ALT >5.0×ULN and ≤20.0×ULN and/or TB >3.0×ULN and ≤10.0×ULN) (Grade 4: AST or ALT >20×ULN and/or TB >10×ULN)	
 
3:
 
For elevations in transaminases 
 
8 × ULN, or elevations in bilirubin
 
5 ×
 
ULN:
 
 
 
Hold study drug/study regimen dose until resolution to Grade
 
1 or baseline
 
 
Resume study drug/study regimen if elevations downgrade to Grade 
 
1 or baseline within 14 days and after completion of steroid taper.
 
Permanently discontinue study drug/study regimen if the elevations do not downgrade to Grade ≤1 or baseline within 14 days
 
For elevations in transaminases 
 
8 × ULN or elevations in bilirubin
 
5 × ULN, discontinue
 
 
 

	
 
Promptly initiate empiric IV methylprednisolone at 1 to 4 mg/kg/day or equivalent.
 
If still no improvement within 3 to 5 days despite 1 to 4 mg/kg/day methylprednisolone IV or equivalent, promptly start treatment with immunosuppressive.
 
therapy (i.e., mycophenolate mofetil). Discuss with study physician if mycophenolate is not available. Infliximab should NOT be used.
 
Perform hepatology consult, abdominal workup, and imaging as appropriate.
 
Once the patient is improving, gradually taper steroids over ≥28 days and consider prophylactic antibiotics, antifungals, and anti-PJP treatment (refer to current NCCN guidelines for treatment of cancer-related infections [Category 2B recommendation]).a
 

<pre>≤20.0×ULN and TB >3.0×ULN and ≤10.0×ULN) (Grade 4: AST or ALT >20×ULN and/or TB >10×ULN)</pre>	$\leq 5 \times ULN:$ • Hold study drug/study regimen dose until resolution to Grade $\leq 1$ or baseline • Resume study drug/study regimen if elevations downgrade to Grade $\leq 1$ or baseline within 14 days and after completion of steroid taper. • Permanently discontinue study drug/study regimen if the elevations do not downgrade to Grade $\leq 1$ or baseline within 14 days For elevations in transaminases $>8 \times ULN$ or elevations in bilirubin $>5 \times ULN$ , discontinue study	
 
4 mg/kg/day methylprednisolone IV or equivalent, promptly start treatment with immunosuppressive.
 
therapy (i.e., mycophenolate mofetil). Discuss with study physician if mycophenolate is not available. Infliximab should NOT be used.
 
Perform hepatology consult, abdominal workup, and imaging as appropriate.
 
Once the patient is improving, gradually taper steroids ov ≥28 days and consider prophylactic antibiotics, antifungals, and anti-PJP treatment (refer to current NCCN guidelines for treatment of cancer-related infections [Category 2B recommendation]).a
 

	1 ( . 1	
	drug/study	
	regimen.	
	Permanently	
	discontinue study	
	drug/study regimen	
	for any case meeting	
	Hy's law criteria	
	(AST and/or ALT	
	$>3 \times ULN +$	
	bilirubin	
	$>2 \times ULN$ without	
	initial findings of	
	cholestasis (i.e.,	
	elevated alkaline P04)	
	and in the absence of	
	any alternative cause. b	
	For Grade 4:	
	Permanently	
	discontinue	
	study	
	drug/study	
	regimen.	

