#### **Cardiac toxicities** For Any Grade: (including arrhythmia, The prompt diagnosis of immune-mediated myocarditis is important, particularly in patients with baseline **Conduction disorder heart** cardiopulmonary disease and reduced cardiac function. Failure, IV dysfunction, Consider, as necessary, discussing with the study **Myocarditis** Any Grade General Guidance \_ physician. Discontinue drug permanently Monitor patients for signs and symptoms of myocarditis upon diagnosis of myocarditis, (new onset or worsening chest pain, arrhythmia, regardless of grade. shortness of breath, peripheral edema). As some symptoms can overlap with lung toxicities, simultaneously evaluate for and rule out pulmonary toxicity as well as other causes (e.g., pulmonary embolism, congestive heart failure, malignant pericardial effusion). A Cardiology consultation should be obtained early, with prompt assessment of whether and when to complete a cardiac biopsy, including any other diagnostic procedures. Initial work-up should include clinical evaluation, BNP, cardiac enzymes, ECG, echocardiogram (ECHO), monitoring of oxygenation via pulse oximetry (resting and exertion), and additional laboratory work-up as indicated. Spiral CT or cardiac MRI can complement ECHO to assess wall motion abnormalities when needed. Patients should be thoroughly evaluated to rule out any alternative etiology (e.g., disease progression, other medications, or infections) Grade 1 -No dose modifications required For Grade 1 (no definitive findings): unless clinical suspicion for Monitor and closely follow up in 2 to 4 days for clinical (asymptomatic with myocarditis is high, in

laboratory (e.g., BNP,EKG,Trop onin) and etiology is unclear )	which case suspected, hold durvalumab-tremelimumab during work- up . -If myocarditis is excluded, resume after complete resolution to Grade 0. - If myocarditis is diagnosed, permanently discontinue durvalumab or tremelimumab	
 
symptoms, BNP, cardiac enzymes, ECG, ECHO, pulse oximetry (resting and exertion), and laboratory work-up as clinically indicated.
 
Consider using steroids if clinical suspicion is high.
 

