### 7.2.6 Hepatic function abnormality

Hepatic function abnormality (as defined previously) in a study subject, with or without associated clinical manifestations, is required to be reported as "hepatic function abnormal" *within 24 hours of knowledge of the event* to the QAM and AstraZeneca/MedImmune Patient Safety using the designated Safety e-mailbox (see 7.3.3.4), unless a definitive underlying diagnosis for the abnormality (e.g., cholelithiasis or bile duct obstruction) that is unrelated to investigational product has been confirmed. If the definitive underlying diagnosis for the abnormality has been established and is unrelated to investigational product, the decision to continue dosing of the study subject

will be based on the clinical judgment of the investigator.

If no definitive underlying diagnosis for the abnormality is established, dosing of the study subject must be interrupted immediately. Follow-up investigations and inquiries must be initiated by the investigational site without delay. Each reported event of hepatic function abnormality will be followed by the treating investigator and evaluated by the PI and AstraZeneca/MedImmune.

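### In Section 4.4, Grade 2 liver injury that meets Hy's law falls under both a resume rule and a permanent-stop rule; the two texts on Grade 2 myocarditis also differ

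*Combined protocol and SAP*

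**What the plan says.** **Liver.** In the hepatitis part of the Section 4.4 table, Grade 2 is defined as "AST or ALT >3.0×ULN and ≤5.0×ULN and/or TB >1.5×ULN and ≤3.0×ULN". The dosing column says to hold, to treat as a higher grade if the event worsens, and otherwise: "If toxicity improves to Grade ≤1 or baseline, resume study drug/study regimen after completion of steroid taper". The row does not mention Hy's law.

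The Hy's law sentence stands in the Grade 3 or 4 cell, just before the Grade 4 instruction. It orders permanent discontinuation "for any case meeting" the criteria: AST and/or ALT above 3×ULN with bilirubin above 2×ULN, no initial cholestasis and no alternative cause.

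Section 7.2.4.4 uses the same two thresholds to define a hepatic function abnormality and refers to the table for management. Section 7.2.6 adds: "If no definitive underlying diagnosis for the abnormality is established, dosing of the study subject must be interrupted immediately". It does not say what follows the interruption.

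**Heart.** The General Considerations let drug resume after a Grade 2 event that settles to Grade 1 or less once the steroid taper is complete. A note there gives myocarditis as an example of a Grade 2 event that ends treatment when "they do not rapidly improve to Grade <1 upon treatment with systemic steroids and following full taper". The Any Grade cell of the cardiac section requires a permanent stop on diagnosis of myocarditis, whatever the grade. The cardiac Grade 2 cell allows a restart only if myocarditis has been excluded. The Grade 1 cell reads "If myocarditis is diagnosed, permanently discontinue durvalumab or tremelimumab", and the Grade 2 cell repeats this. Most other rows in the table refer to the study drug or study regimen.

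**The concern.** An investigator who grades an event as 2 and follows that row is told to resume. A colleague who knows the Hy's law sentence is told never to resume. Both are following the protocol. The table gives no order of precedence between its rows, or between the General Considerations and the event-specific sections.

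What is at stake is re-exposure after a toxicity that the protocol treats as dangerous. It singles out Hy's law cases for permanent discontinuation and describes myocarditis as carrying a high likelihood of morbidity or death. Decisions could differ between investigators, or between visits, at the single center.

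**Working it through.** The plan states no figure to reproduce. The check is an overlap of threshold ranges and a comparison of texts.

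**1. Liver overlap** (all values ×ULN)

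| | Grade 2 row | Hy's law sentence | Both |
|---|---|---|---|
| AST or ALT | >3 to ≤5 | >3 | >3 to ≤5 |
| Bilirubin | >1.5 to ≤3 | >2 | >2 to ≤3 |

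The overlap is not empty, and inside it both tests are Grade 2. Above it, the event is Grade 3 or 4. Below it, Hy's law is not met.

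Worked case: ALT 4, bilirubin 2.5, normal alkaline phosphatase, no other cause.
- Grade: 3 < 4 ≤ 5 and 1.5 < 2.5 ≤ 3, so Grade 2. Outcome: hold, then resume.
- Hy's law: 4 > 3 and 2.5 > 2, with both qualifiers met. Outcome: permanent stop.
- Section 7.2.6: interrupt, with the next step not stated.

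**2. Does the placement of the sentence settle it?** The Grade 3 cell has its own hold-and-resume path, for transaminases up to 8×ULN or bilirubin up to 5×ULN. The Hy's law sentence therefore has a function within Grade 3 alone, and a reader need not take it as reaching back into Grade 2. The same table shows how a rule across grades can be placed: the cardiac section uses its Any Grade cell, and the block for hepatocellular carcinoma patients, which does not apply here, puts a rule on combined transaminase and bilirubin rises after the graded rows. The Any Grade cell for hepatitis has no Hy's law text.

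**3. Does the delay limit catch the case anyway?** Sections 4.5 and 4.7 stop treatment after a delay of more than 4 weeks (28 days) for related toxicity. In the Grade 2 row, steroids start if the event worsens or lasts more than 3 to 5 days, and the taper lasts at least 28 days.
- For an event treated because it persisted, the shortest hold is about 3 + 28 = 31 days.
- Assume that delay is counted from the missed dose, which the plan does not define. With 2-weekly MEDI4736, a dose due at onset is then 31 days late (limit exceeded), and a dose due 14 days after onset is 31 − 14 = 17 days late (limit not reached).
- An event that settles before steroids are needed has no taper to complete.

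The limit will catch some cases and not others.

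**4. Myocarditis, Grade 2, diagnosed, improving rapidly on steroids and after full taper**

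| Text | Outcome |
|---|---|
| General Considerations, Grade 2 rule | may resume |
| General Considerations, Grade 2 note | condition for permanent stop not met |
| Cardiac section, Any Grade and Grade 2 | permanent stop |

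**5. Arm 3.** The Grade 1 cardiac cell names the two agents jointly for the hold during work-up, then joins them with *or* for the permanent stop. For a patient on both, that can be read as one agent or as both.

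**The case against.** The strongest reply on the liver is that the Hy's law sentence is worded to cover every case and carries its own thresholds, so it is the exception and the Grade 2 row the general rule. That is a fair reading. The defect is then one of placement and a missing cross-reference. But a reader of the Grade 2 row cannot see the exception, and nothing says that it overrides that row.

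There are also backstops. Section 7.2.6 sends these liver events to the quality monitor and the drug supplier within 24 hours unless an unrelated cause is confirmed, and the principal investigator and the supplier evaluate them. This lowers the chance of an unnoticed restart. It does not say what they should decide.

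On the heart, the cardiac rows never allow a restart after diagnosed myocarditis. Permission to resume is an inference from the general text, which is permissive, and a permissive general rule and a mandatory specific stop can both be obeyed by stopping. The General Considerations describe their stop conditions as additional to the graded criteria, which supports that reading, and the Amendment 6 entry in Appendix D describes a permanent stop on diagnosis. This limb is therefore secondary. It remains because a condition attached to stopping has no purpose if stopping is unconditional.

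On Arm 3, *or* may simply span the arms, since the table serves both monotherapies and the combination. That is plausible but not stated.

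A reader might infer more than the documents support:
- **Different sites acting differently.** The trial is single-center, so the divergence is between investigators or visits.
- **A distorted comparison of discontinuation rates between arms.** Sections 2.2.1 and 6.2 define safety by the number, frequency and severity of adverse events, and Section 10.3 plans only summaries. No discontinuation-rate endpoint and no between-arm safety test is specified.
- **A third, conflicting liver outcome in Section 7.2.6.** Interruption is a first step and is compatible with a later permanent stop. Its definition is also broader than Hy's law.
- **A conflict at Grade 3 myocarditis.** The general Grade 3 note already agrees with the cardiac rows.

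**Conclusion.** The liver conflict is in the current text. For AST or ALT above 3 and up to 5×ULN with bilirubin above 2 and up to 3×ULN, no cholestasis and no other cause, following the Grade 2 row as written gives the opposite outcome to the Hy's law sentence. The myocarditis mismatch is real but weaker: it lies between the general Grade 2 text and the cardiac section, and depends on an inference from the former. The Arm 3 wording is an ambiguity.

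The documents give no expected frequency for either event in this population. With at most 45 patients, the numbers are likely to be small. The consequence is inconsistent re-dosing decisions at one center, not a bias in a planned analysis. The conclusion rests on reading the Hy's law sentence as part of the Grade 3 or 4 cell, where the extracted table places it, and on the absence of any precedence rule. It takes no view on which clinical outcome is right.

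**What to change.** Reconcile the passages so that each case has one outcome. The sponsor and drug supplier decide which.

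1. State the Hy's law outcome once, outside the graded hepatitis rows, and cross-refer to it from the Grade 2 row and from Section 7.2.6, which should also say what follows interruption.
2. Make the Grade 2 note on myocarditis in the General Considerations agree with the cardiac section. The Grade 3 note needs no change.
3. In the cardiac rows, state which agent or agents the permanent stop covers in Arm 3.
4. Add one line saying which text governs when the general and event-specific sections differ.

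The cost is table wording in the next amendment and a memo to the investigators. It needs no new data, assessments or patients.
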